5.1 Study Assessments

5.1.1 Informed Consent

The parent or legal guardian of a potential subject will be given a verbal explanation of the study and the procedures involved and will have all questions addressed. The subject's parent or legal guardian must sign and date a consent form that has been approved by the appropriate institutional review board/independent ethics committee (IRB/IEC) before the screening procedures are initiated. The subject's parent or legal guardian will be given a copy of the signed and dated informed consent form.

5.1.2 Subject Eligibility

All subjects will be assessed for eligibility against the inclusion and exclusion criteria described in Section 4.3 and Section 4.4 and background clinical information collected.

Page 37 of 76

5.1.3 Medical History

Complete medical history, including prenatal, birth history, family history and disease history will be recorded at Screening.

5.1.4 Demographic Information

The following demographic information will be collected at Screening: date of birth, birth weight, gender, race and ethnicity.

5.1.5 Anthropometrics

Anthropometrics, including weight, recumbent length (subjects ≤2 years of age at the time of examination) or height (subjects >2 years of age at the time of examination), head circumference, mid-upper arm circumference, and abdominal circumference, will be measured at the timepoints specified in Appendix A.

Refer to the SOM for a detailed description of the procedure for each anthropometric measurement.

Percentiles or z-scores for WFA, WFL/WFH, LFA/HFA, HCFA, and MUACFA will be determined based on WHO child growth standards (WHO Multicentre Growth Reference Study Group, 2006 and 2007). Growth status will also be classified according to 3 dichotomous indicators: underweight (<-2 standard deviations [SD] from the median for WFA), wasting (<-2 SD from the median for LFA/HFA).

5.1.6 Physical Examination

A physical examination will be performed by the Investigator or qualified designee at the timepoints specified in Appendix A. The examination will include an assessment of the subject's general appearance, skin, head, eyes, ears, nose, and throat, heart, lungs, abdomen, extremities/joints, and neurological status. Whenever possible, the same person should perform the physical examination at each study visit. Abnormal findings will be captured in the eCRF.

Every physical examination will also include the following:

- Liver size: A clinical assessment of liver size (palpable/non palpable and centimeters below costal margin), regularity (smooth/nodular) and sensitivity (tender/non tender) will be made.
- **Spleen size:** A clinical assessment of spleen size (palpable/non palpable and centimeters below costal margin), regularity (smooth/nodular) and sensitivity (tender/ non-tender) will be made.
- **Lymphadenopathy:** An assessment of the size, location, and character of any palpable lymph nodes will be made. Areas to be examined include: cephalic (occipital, preauricular, postauricular, submental, submandibular), cervical, clavicular, axillary, and inguinal. Any enlarged nodes will be characterized as tender or non-tender.

• **Digital Photograph:** A digital photographic image of the subject in a supine position (full length and abdominal close up) will obtained during selected physical examinations, as specified in Appendix A.

Refer to the Site Operations Manual (SOM) for a detailed description of the physical examination procedure and instructions for photographs.

5.1.7 Abdominal Ultrasound

Abdominal ultrasonography will be performed at the timepoints specified in Appendix A to measure the liver and spleen size.

Abdominal ultrasonography will be performed by a qualified person, and results will be interpreted by a radiologist trained in ultrasonography.

5.1.8 Abdominal MRI

Abdominal MRIs should be considered at the timepoints specified in Appendix A to provide a more accurate quantification of liver and spleen volume. If an Abdominal MRI cannot be performed, an Abdominal Ultrasound will be performed instead at that timepoint.

Investigators are encouraged to obtain abdominal MRIs in subjects receiving general anesthesia or sedation for other procedures at a scheduled imaging timepoint. To allow flexibility in scheduling MRIs, a broad time window is given for each MRI assessment in Appendix A. For example, the baseline MRI may be obtained at any time from Screening through the Week 0 study visit.

Because MRI can provide important information on liver and spleen volume that can be related to expected normal values abdominal MRIs should be obtained during the treatment phase, even if a subject did not provide a baseline MRI.

All imaging scans will be acquired and the results interpreted by a magnetic resonance technician or other qualified individual using standardized imaging protocols.

Refer to the Imaging Manual for instructions on image acquisition and analysis.

5.1.9 Vital Signs

Vital signs will include pulse rate, respiratory rate, systolic and diastolic blood pressure and core body temperature (rectal or oral). Assessment of pulse rate and blood pressure will be taken after the subject has been in a supine position.

Vital signs will be measured at the timepoints specified in Appendix A. On dosing days, vital signs will initially be recorded pre-infusion, every 15 (\pm 5) minutes during infusion and every 30 (\pm 10) minutes from 0 to 4 hours after completion of the infusion. Once a subject has received a stable dose for at least 2 months, with no moderate-to-severe IARs, vital signs will be recorded pre-infusion and every 30 (\pm 10) minutes during infusion and from 0 to 4 hours after completion of the infusion. After a subject has successfully completed at least 1 year of treatment with no occurrence of moderate-to-severe IARs, the post-infusion period for vital sign monitoring may be shortened from 4 hours to 2 hours.

Page 39 of 76

Additional readings may be taken at the discretion of the Investigator and in the event of an IAR.

5.1.10 Electrocardiogram

An age-appropriate 12-lead electrocardiogram (ECG) will be obtained at Screening and reviewed by a qualified clinician. Additional age-appropriate 12-lead ECGs may be obtained at subsequent study visits, if clinically indicated. Any abnormalities identified by the clinician will be specified as clinically significant or not clinically significant.

5.1.11 Laboratory Assessments

Blood and urine samples for laboratory tests will be collected at the timepoints specified in Appendix A.

Prior to any dose change, serum lipid, serum liver, hematology, chemistry, ferritin and hs-CRP shall be obtained. Serum lipid and serum liver assessments should be taken 4, 8, and 12 weeks following any study drug or lipid drug dose change.

Due to the limitations on the volume of blood collection that is considered to be acceptable in young children with very small total circulating blood volumes (see Section 5), the laboratory samples will be ranked in the order corresponding to the study objectives, as shown in Table 2. Only Tier 1 assessments are considered mandatory and all efforts should be made to collect these in all subjects. Samples for the Tier 2 and Tier 3 assessments will only be collected if the blood volume threshold for subject's weight, as well as the subject's clinical status, permit (see Section 5 for further details).

Tier 1 (Mandatory)	
CBC/Hematology:	White blood cell count, red blood cell count, hemoglobin, hematocrit, MCV, MCH, MCHC, platelet count, neutrophil, lymphocytes, monocytes, eosinophils, basophils, peripheral smear for examination of cell morphology
Chemistry Panel:	Glucose, urea nitrogen, creatinine, sodium, potassium, chloride, calcium, magnesium, inorganic phosphorus, total protein, lactate dehydrogenase
Liver Function Tests:	AST/SGOT, ALT/SGPT, alkaline phosphatase, GGT, albumin, bilirubin (direct, indirect, total)
Anti-drug Antibody:	Anti- sebelipase alfa antibody
Urinalysis:	pH, glucose, ketones, blood, protein, nitrite, and leukocytes (microscopic examination will only be done if blood, nitrite and/or leukocytes are abnormal)

Table 2Clinical Laboratory Tests, By Tier

Page 40 of 76

Coagulation Studies:	PT (INR), aPTT					
DNA Sample	See Section 5.1.15					
LAL Enzyme Activity	See Section 5.1.16					
Tier 2 (Optional)						
Lipid Panel:	Total cholesterol, triglyceride, HDL, LDL					
Other Chemistry:	Serum ferritin					
Tier 3 (Optional)						
Pharmacokinetic Assessments	See Section 5.1.14					
Exploratory Biomarkers	See Section 5.1.13					

Coagulation studies are required at Screening only. Thereafter, they should be completed only if the preceding assessment was abnormal or if it is clinically indicated based on emerging evidence of liver dysfunction.

Laboratory reports will be reviewed by the Investigator, or designee, and any abnormalities will be specified as clinically significant or not clinically significant. In the event of unexplained clinically significant abnormal laboratory test values, the tests should be repeated as soon as possible (preferably within 24 hours) and followed up until they have returned to within the normal range and/or an adequate explanation has been identified.

Refer to the laboratory manual for further details regarding the collection, processing, and storage of these samples.

5.1.12 Denver II Developmental Screening Test

The Denver II will be administered at the timepoints specified in Appendix A.

The Denver II is a standardized measure to assess development in children from 1 month to 6 years of age (Frankenberg, 1992, *Pediatr*). The Denver II includes performance-based and parent-reported items in 4 functional areas: fine motor-adaptive, gross motor, personal-social, and language skills. The test was normed on a diverse sample of children who were full term and had no obvious developmental disabilities; the norms indicate when 25%, 50%, 75%, and 90% of children passed each item. The Denver II has good inter-rater and test-retest reliability (correlations \geq 0.90 for most tests).

The Denver II must be administered by a trained clinician and takes an average of 10 to 20 minutes to complete. Administration and scoring of the Denver II is based upon the child's age. (Note that for premature infants, the number of months premature is subtracted from the infant's chronological age.) For each test item administered, the clinician determines if the child's response falls within or outside of the normal expected range of success on that item for the child's age. The interpretation of the individual test items is then used to classify the child's development in each functional area and for the overall test.

Page 41 of 76

5.1.13 Exploratory Biomarkers

Whenever feasible, based on the blood volume threshold for the subject's weight, a blood sample for serum isolation (2 aliquots) will be obtained at the timepoints specified in Appendix A. The serum sample will be used to identify baseline disease and dynamic markers that will help better understand the pathogenesis of LAL Deficiency, related comorbidities and response to treatment. Given the rarity of LAL Deficiency and the paucity of information on disease characteristics, the definitive list of analytes remains to be determined.

Refer to the laboratory manual for further details regarding the collection, processing, and storage of these samples.

5.1.14 Pharmacokinetic Assessments

To reduce risk of iatrogenic anemia, PK sampling may be limited. In order of importance samples will be collected to derive C_{max} and CL.

PK samples should not be taken from the same extremity where the infusion catheter is in place. Sampling for measurement of sebelipase alfa serum levels will be performed during the study visits indicated in Appendix A. These samples will be collected within designated time windows, rather than at discrete timepoints, to allow more flexibility in the management of PK sampling in these subjects and to provide opportunities for measurement of drug concentrations across a broader timeperiod with limited sampling.

In all subjects:

- 0 to 1 hours after the start of the infusion;
- Between 1 hour after the start of the infusion and the end of the infusion (i.e. when the infusion bag has been emptied, but prior to the sodium chloride flush).

In those subjects for whom the thresholds for allowed blood collection volumes have not been exceeded:

- 0 to 0.5 hours after completion of the infusion;
- 0.5 to 1 hour after completion of the infusion;
- 1 to 2 hours after completion of the infusion.

All PK samples, at time points that coincide with a vital sign assessment, will be taken before cuff inflation for blood pressure assessment on the non-infusion arm. PK samples at other time points will be taken at least 5 minutes after cuff deflation.

Refer to the laboratory manual for further details regarding the collection, processing, and storage of these samples.

5.1.15 DNA Sample

The Sponsor intends to apply pharmacogenetics to the sebelipase alfa program in order to explore how genetic variations may affect clinical parameters associated with sebelipase alfa use and acid lipase biology. DNA sequences, including both the protein coding sequence and

Page 42 of 76

sequences that regulate gene transcription, messenger ribonucleic acid (mRNA) stability and the efficiency of protein translation that may be investigated include:

- 1. LAL (LIPA);
- 2. Genes coding for other proteins involved in lipid biology that may contribute to and/or modify the disease phenotype of LAL Deficiency, e.g. ABCA1;
- 3. Genes that may modify susceptibility to any sebelipase alfa related AEs.

Where possible and in compliance with local regulations, a blood sample for DNA extraction will be collected from the subject at Screening or as soon as practically possible thereafter based on blood volume collection threshold, unless a stored DNA sample is already available for the subject. The DNA will be stored and used as part of a later pooled analysis. This will include determining the spectrum of LAL mutations in subjects with growth failure due to LAL Deficiency and the relationship between gene mutation, safety, efficacy and susceptibility to anti-sebelipase alfa antibody development.

If feasible, a blood sample for DNA extraction and testing of the LAL gene mutations will be collected from the subjects' biological parents after a separate consent has been obtained.

The Sponsor will only analyze DNA sequences within genes relevant to the mode of action and response to sebelipase alfa, including variants important in understanding AEs, and candidate genes with a potential role in the etiology, pathogenesis, and progression of LAL Deficiency.

Samples will be stored by the Sponsor, or designee, in a secure, monitored, and controlled environment. No additional testing will be performed on the samples collected in the study.

Refer to the laboratory manual for further details regarding the collection, processing, and storage of these samples.

5.1.16 LAL Enzyme Activity

Study inclusion will be contingent on documented decreased LAL activity relative to the normal range of the lab performing the assay or a documented result of molecular genetic testing confirming a diagnosis of LAL Deficiency.

Blood samples will also be collected at Screening to measure LAL activity in peripheral blood mononuclear cells (PBMCs) and in a dried blood spot (DBS) collected on filter paper to ensure consistency of LAL activity measurement in all subjects. In the unlikely event of a discrepancy between the diagnosis of LAL Deficiency based on baseline LAL activity in PBMCs and/or DBS and the previously documented diagnosis, a subject may be discontinued from the study and may be replaced.

5.1.17 Liver Biopsy

An optional liver biopsy will be obtained for evaluation of hepatic histology after at least 1 year of treatment, at the timpoints suggested in Appendix A. Biopsies will be performed only with consent from the subject's parent/guardian and where local regulations permit, and are subject to discretionary approval from each center's IRB/IEC.

Page **43** of **76**

Liver biopsy procedures should be performed according to the local institutional practices by a qualified professional.

All biopsies collected in this study will be centrally evaluated by a pathologist with the appropriate expertise. This evaluation will include an assessment of the overall disease activity as well as a description of specific histopathological features of the disease.

Page 44 of 76

6 Investigational Medicinal Product

6.1 Description of IMP

Details of the non-clinical experience to date with sebelipase alfa, as well as IMP stability information, can be found in the current version of the Investigator Brochure (IB). Sebelipase alfa must be administered under close supervision of the Investigator, or designee.

Sebelipase alfa is provided in single dose 10 mL glass vials. The solution (total 10.5 mL including 5% overfill) has an approximate concentration of 2 mg/mL. Exact concentration will be on the individual vials.

Sebelipase alfa contains no preservatives and vials are single use only.

Sodium chloride (0.9%) for injection, for use in preparation of diluted solutions for infusion, will be sourced locally by the study center.

6.2 Method for Assigning Subjects to Treatment Groups

No randomization schemes will be employed; all subjects will receive the same starting dose of sebelipase alfa in this study.

Each subject will be assigned an enrollment number after informed consent has been obtained from the subject's parent or legal guardian. This enrollment number will be used to identify the subject throughout his/her participation in the study.

A subject who does not meet all study eligibility criteria due to a potentially transient condition observed at screening (e.g., discontinuation of another investigational medicinal product within 14 days, or failure to meet protocol-defined growth failure criteria in a subject <6 months of age), will be allowed to return for re-screening.

6.3 Storage and Disposition of IMP

6.3.1 Receipt of IMP

Upon receipt of the IMP, an inventory must be performed and verified by the person accepting the shipment. It is important that upon IMP delivery the designated study staff counts and verifies that the shipment contains all the items noted in the shipment inventory. Any damaged or unusable IMP in a given shipment will be documented in the study files. The Investigator must notify study Sponsor of any damaged or unusable IMP that was supplied to the Investigator's site.

6.3.2 Storage

All sebelipase alfa vials must be stored under controlled refrigerated conditions at $2^{\circ}C$ to $8^{\circ}C$ ($36^{\circ}F$ to $46^{\circ}F$). (Note: temperature excursions up to $25^{\circ}C$ for up to 12 hours have not been shown to be associated with loss of enzyme activity.) Vials should not be frozen and should be protected from light during storage.

The infusion bag or syringe containing sebelipase alfa diluted in 0.9% sodium chloride should be prepared just prior to the start of infusion administration. For study sites where there is a requirement for dilution at a separate location this needs to be done in a place with controlled and aseptic conditions. Although the infusion bag or syringe is stable at room temperature $(23^{\circ}C \text{ to } 26^{\circ}C)$ for 12 hours, it should be used as soon as possible after preparation.

6.3.3 Disposition

The Investigator or designated person (e.g. a licensed pharmacist) will be responsible for maintaining accurate records for all IMP used. Opened sebelipase alfa vials still containing any residual volume may be stored at room temperature for IMP accountability. Following IMP accountability, the Sponsor or designee will give written authorization to the Investigator to return or destroy any remaining IMP as instructed.

6.4 Preparation and Administration of IMP

Under no circumstances will the IMP be used other than as directed in the protocol.

6.4.1 Preparation of IMP

The infusion bag (or syringe) containing sebelipase alfa will be prepared just prior to the start of infusion administration. Prior to preparation of the infusion, the vials of study drug will be visually inspected. The solution should not be used if it contains foreign particulate matter or is discolored. The solution may be used if a small number of visible translucent to opalescent or white amorphous or threadlike particles are present in the vial. The contents should NOT be warmed using a microwave or other heat source. Sebelipase alfa is a protein and will be handled and mixed gently to prevent foaming.

If subject's weight cannot reliably be obtained on the morning of the infusion then the subject's most recent weight measurement within 7 days, rounded to the nearest 0.1 kg, will be used for calculating the volume of study drug to be withdrawn from the vial(s) to prepare the infusion.

Sebelipase alfa should be diluted to a concentration of 0.1 to 1.5 mg/ml for infusion. Refer to the IMP manual for detailed instructions regarding preparation.

6.4.2 Administration of IMP

Sebelipase alfa should not be infused with other products in the same infusion tubing, as the compatibility in solution with other products has not been evaluated. IMP infusions will be administered at an infusion rate depending on the subject's weight, and must be administered under close supervision of the Investigator, or designee. Sebelipase alfa should not be administered at an infusion rate exceeding 4 ml/kg/hr. For detailed administration instructions please refer to the IMP manual.

Subjects who are medically stable, as determined by the Investigator, may transfer to a local medical center for long-term treatment, contingent upon the local medical center being appropriately qualified and securing the required regulatory and IRB/IEC approvals. Scheduled

study assessments may also be performed at a local medical center with access to the appropriate facilities and expertise.

6.5 Infusion Associated Reactions

Infusion-associated reactions will be considered AEs of special interest. Any AE that occurs during the infusion or within 4 hours after the IMP infusion is completed and is assessed by the Investigator as at least possibly related to IMP will be designated as an IAR. In addition, if, at any time during the study, the Investigator observes symptoms that he/she considers to be consistent with an IAR or hypersensitivity reaction related to administration of study drug, the symptoms should be recorded as an AE(s) and designated as an IAR(s). Individual adverse event terms should be recorded rather than the terms, IAR or Infusion Associated Reaction.

As with any ERT, medications and equipment for the treatment of hypersensitivity reactions must be available for immediate use in case of unexpected, severe hypersensitivity reactions. These supplies include, but are not limited to, oxygen, acetaminophen, antihistamines (e.g., diphenhydramine, parenteral and oral [PO]), corticosteroids, epinephrine and cardiopulmonary resuscitation devices.

General guidelines for classifying the severity of a reaction are provided in Section 7.1.1.

For similar biological products, most acute IARs occur within 2 hours of the infusion. Signs of a possible acute IAR may include:

• Hyperemia (flushing), fever and/or chills, nausea, pruritus, urticaria, gastro-intestinal symptoms (vomiting, diarrhea, abdominal cramping) cardiopulmonary reactions, including chest pain, dyspnea, wheezing, stridor, hypotension or hypertension.

If any of the above signs and symptoms are observed during the infusion and the subject remains hemodynamically stable:

- The infusion rate must be slowed by 50% (reduced to half the rate being given at the onset of the event, e.g. from 10 mL/hr to 5 mL/hr) and the infusion time extended in accordance with the institutional standard of care. The infusion rate may be decreased further by 25% if symptoms persist. If the event resolves, the infusion should continue for a minimum of 30 minutes at the reduced rate before the rate is increased to 75% of the original rate on the infusion schedule. If the subject tolerates infusion at 75% of the original rate for at least 30 minutes the original rate may be restored for the remainder of the infusion.
- In accordance with institutional standard of care for subject's age, treatment with oral anti-pyretic and/or antihistamine should be considered.

In subjects who experience severe IAR with clinically significant cardiovascular effects (e.g., hypertension or hypotension defined as a decline approaching 20-30% of their preinfusion value without alternative etiology, agitation, pain, fluid overload, dehydration), respiratory symptoms (significant shortness of breath, stridor, wheezing, laryngeal edema or swelling of tongue),

Page 47 of 76

cardiac arrhythmias, or anaphylactic/anaphylicatoid shock with hypotension and circulatory collapse:

- The infusion should be stopped.
- The subject should be treated with oxygen if available, IV antihistamines, corticosteroids, and IM epinephrine, if necessary, in accordance with institutional standard of care for the subject's age.
- Dosing of the subject will be suspended until the Safety Review Committee has completed review of the IAR, and any other relevant safety data.
- Subjects who experience a moderate or severe IAR should have a serum sample collected for tryptase 1-3 hours after the IAR onset and another serum sample for tryptase and ADA during the next study visit (≥4 days after the IAR) prior to the infusion. Skin testing may be considered.

Additional details on the management of subjects with infusion reactions are outlined in the table in Appendix B.

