7.1 Adverse Events and Laboratory Abnormalities

7.1.1 Clinical Adverse Events

Adverse Event

An *Adverse Event* is any untoward medical occurrence in a subject which does not necessarily have to have a causal relationship with the administration of an IMP. An AE can therefore be any unfavorable and unintended sign, symptom or disease temporally associated with the use of the IMP, whether or not considered related to the medicinal product. Pre-existing conditions that worsen in severity during the course of the study are to be reported as AEs.

All AEs occurring during the clinical study will be reported on the AE page of the eCRF as described in Section 7.3.

The Investigator will assess the severity, causality (relationship to IMP), and seriousness of each AE.

Severity: The severity of AEs will be graded according to the National Cancer Institute Common Terminology Criteria for Adverse Events (CTCAE), version 4.0 or higher. The CTCAE displays Grades 1 through 5 with unique clinical descriptions of severity for each AE based on the general guideline below. Detailed instructions on grading of events by Medical Dictionary for Regulatory Activities (MedDRA) system organ class and lower level term are available online.

- **Grade 1** Mild; asymptomatic or mild symptoms; clinical or diagnostic observations only; intervention not indicated.
- **Grade 2** Moderate; minimal, local or noninvasive intervention indicated; limiting age-appropriate instrumental activities of daily life (e.g., preparing meals, shopping for groceries or clothes, using the telephone, managing money).
- **Grade 3** Severe or medically significant but not immediately life-threatening; hospitalization or prolongation of hospitalization indicated; disabling; limiting self-care activities of daily life (e.g., bathing, dressing and undressing, feeding self, using the toilet, taking medications, and not bedridden).
- **Grade 4** Life-threatening consequences; urgent intervention indicated.
- **Grade 5** Death related to AE.

Causality: AEs will be assessed by the Investigator as not related, unlikely related, possibly related, or related to IMP. Table 3 provides general guidance on the assessment of causality. Assessment of causality should be based on the Investigator's medical judgment and the observed symptoms associated with the event. For data reporting purposes, related AEs will be

Page **49** of **76**

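### For a moderate infusion reaction in a hemodynamically stable infant, Section 6.5 orders the rate halved and Appendix B orders the infusion stopped; nothing says which governs

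*Protocol*

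**What the plan says.** Protocol Section 6.5 lists possible signs of an acute IAR, among them flushing, pruritus, urticaria, gastrointestinal symptoms and chest pain. It then sets a condition: "If any of the above signs and symptoms are observed during the infusion and the subject remains hemodynamically stable". The consequence is mandatory: "The infusion rate must be slowed by 50" percent. For persisting symptoms, "The infusion rate may be decreased further by 25% if symptoms persist". On medication, "treatment with oral anti-pyretic and/or antihistamine should be considered". The next paragraph deals with severe IARs and contains the section's only instruction to stop. Moderate reactions are mentioned only for blood sampling: "Subjects who experience a moderate or severe IAR should have a serum sample collected for tryptase 1-3 hours after the IAR onset".

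Appendix B grades reactions as mild, moderate or severe. Its Moderate row covers flushing, chest discomfort, itching or an urticarial rash, severe headache and gastrointestinal symptoms. The first action there is to stop the infusion. An intravenous antihistamine follows, with intravenous steroids to be considered. The infusion may restart at half the original rate once the event has resolved.

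Section 6.5 introduces this table with "Additional details on the management of subjects with infusion reactions are outlined in the table in" Appendix B.

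**The concern.** A moderate reaction in a stable infant falls under both instructions, and their first actions cannot both be carried out. A team following the body text keeps infusing the suspected cause at half rate and thinks about an oral drug. A team following the appendix halts the infusion and gives intravenous treatment.

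The subjects are fragile infants, and the protocol treats IARs as events of special interest. Under Section 6.4.2, treatment may also move to local medical centers, so several teams may have to apply these instructions. At stake is safe and uniform conduct of infusions. The survival estimate is not at stake.

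**Working it through.** There is no planned figure to reproduce; the check is a comparison of texts.

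**1. Do the two rules reach the same reactions?** Flushing, itching or urticaria, and gastrointestinal symptoms appear both in the Section 6.5 list and in Appendix B's Moderate row. The Moderate row names no blood-pressure sign; hypotension and circulatory collapse are in the Severe row. A moderate reaction as tabulated will therefore usually meet Section 6.5's stability condition.

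**2. What does each text require?**

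| | Section 6.5, stable subject | Appendix B, Moderate row |
|---|---|---|
| First action | Halve the rate and continue | Stop |
| Medication | Oral antipyretic and/or antihistamine, to be considered | Intravenous antihistamine; intravenous steroids to be considered |
| Running at half rate | At once, during the reaction | Only after resolution |

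**3. Worked case.** Section 6.5 uses 10 mL/hr as its example. Suppose a stable infant receiving that rate develops an urticarial rash judged moderate.
- Section 6.5: 10 × 0.5 = 5 mL/hr immediately.
- Appendix B: 0 mL/hr, then 10 × 0.5 = 5 mL/hr once the rash has resolved.

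**4. Does any text settle it?**
- Section 6.5 presents Appendix B as further detail. Stopping in place of a mandatory slowing is a replacement, not a detail.
- Section 6.5 says must, whereas Appendix B is titled as recommendations. On the other side, Appendix B is the more specific text. The protocol draws neither conclusion.
- Section 7.5 covers suspension on the Safety Committee's recommendation. Appendix C covers IARs of Grade 3 or higher. Neither reaches a moderate reaction.
- SAP Section 10.1 defines infusion reactions for analysis and does not deal with their management.
- On severity, Section 6.5 points elsewhere: "General guidelines for classifying the severity of a reaction are provided in Section 7.1.1". That section uses CTCAE, whose Grade 1 reads "Mild; asymptomatic or mild symptoms; clinical or diagnostic observations only; intervention not indicated". This does not fit Appendix B's mild tier, which is managed by slowing and oral medication, so the CTCAE grades cannot simply stand in for the table's tiers.

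**The case against.** The strongest reply is that the intention can be inferred. The stable branch of Section 6.5 follows Appendix B's Mild row almost step by step, and its severe paragraph matches the Severe row. On that view the section summarizes the two ends of the table, the appendix supplies the middle, and specific text prevails over general text. This is a plausible account of what was meant. It does not remove the conflict: the condition in Section 6.5 is hemodynamic stability, not mildness, and the action is mandatory.

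A second reply is that the list in Section 6.5 also contains dyspnea, wheezing and stridor, so a literal reading would put some severe reactions under the halving rule too. A reader might infer that the severe tier is equally in conflict. The documents do not support that. The next paragraph of the same section takes severe IARs, including those respiratory signs, separately and says to stop, and Appendices B and C agree. For moderate reactions Section 6.5 has no such paragraph.

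A third reply concerns consequence. Infusions are closely supervised, emergency drugs must be at hand, and both texts defer in part to institutional standards of care. The IMP manual cited in Section 6.4.2 is not available here and may carry its own algorithm. All of this stands and limits what can be said about harm.

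Finally, Appendix B's own tiers overlap: flushing is in both the Mild and Moderate rows, and chest discomfort is separated only by the word mild. That also stands, and the fix has to deal with it.

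**Conclusion.** The point holds for moderate reactions in stable subjects and should be fixed. The protocol gives a mandatory instruction in its body and an incompatible one in its own table, with no rule of precedence. Confidence is high on the wording. The documents give no frequency of moderate reactions, so no number of affected infusions or harmed subjects can be claimed.

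Two stronger readings should be resisted.
- A reader might infer a second contradiction because Section 6.5 has no stop step when mild symptoms persist, while Appendix B's Mild row does. This is an omission. Section 6.5 does not forbid stopping, and the table it refers to supplies the step.
- A reader might infer damage to the efficacy result. The Primary Efficacy Analysis Set depends on having received any amount of drug and on age at first infusion, and the endpoint is survival to 12 months of age. Slowing or pausing an infusion changes neither definition, and the primary survival analysis stays as planned.

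The conclusion assumes that no document outside the protocol and SAP formally overrides Section 6.5. Even if the IMP manual did, the protocol would still contradict itself.

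**What to change.** Amend Section 6.5 as follows:
1. Limit the halving rule to reactions that are mild under Appendix B.
2. Add that moderate reactions follow Appendix B: stop, treat, and resume at half the original rate only after resolution.
3. State that Appendix B's tiers govern infusion actions.
4. State that when the tier is in doubt, as with flushing or chest discomfort, the more cautious row applies.

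Repeating Appendix B's stop step for persisting mild symptoms in Section 6.5 would be a sensible alignment, but it is optional.

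The cost is a short text amendment and a few more paused infusions. There is no statistical cost.
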